A comparative study of electric toothbrushes for the efficacy of single use plaque removal and the effect on plaque accumulation and gingivitis.

[name]; [name]; [name]; [name]

NCT03416985

November 15, 2019

A comparative study of electric toothbrushes for the efficacy of single use plaque removal and the effect on plaque accumulation and gingivitis.

[name]; [name]; [name]; [name]

It is well accepted that the greatest contributor to the health of the periodontium and dentition is regular and thorough dental plaque removal, typically by means of adequate toothbrushing. Although patients are typically informed about the risks of substandard oral hygiene and the contributing factors in oral/dental disease by dental professionals, research has shown that an undesirably high proportion of adults find thorough toothbrushing with a standard manual toothbrush to achieve a plaque-free state challenging, as evidenced by high worldwide levels of gingivitis and/or periodontitis.

The purpose of this study is to clinically evaluate the plaque removal efficacy of two electric powered toothbrushes after a single use, as well as the effect on plaque accumulation and gingivitis after 14 days and 30 days period.

Materials and Methods

Study design: randomised, single blinded, parallel.

After the screening procedure and based on inclusion requirements, all subjects will receive oral prophylaxis (T0) to ensure a baseline of 0 Plaque Index (PI) prior to the first appointment (T1). The subjects will be instructed not to use a tooth brush or any mechanical cleaning device until the initial PI and Gingival Indexes (GI) are taken at 24 hours after T0.

The subjects will be randomized into 3 groups, and they will be provided one of the two evaluated toothbrushes, as well as toothpaste. All subjects will be using identical toothpaste and will receive oral hygiene instructions based on the manufacturer's recommendations.

At T1 initial GI and PI will be taken prior to brushing followed by a second PI reading immediately after the first use of the power driven toothbrush.

The subjects will be instructed to brush twice a day for a period of 2 minutes (following the programmed toothbrush timer) and refrain from using dental floss, tooth pick or any mechanical oral hygiene aid for the period of the study.

On the second visit at 14 days (T2) and third visit at 30 days (T3), additional GI and PI readings will be taken and data will be recorded. All measurements and clinical examinations will be performed by a single blinded examiner. Evaluation on teeth will be made on six teeth #3,7,12,19,23 and 28 (mesio-buccal, buccal, disto-buccal and mesio-lingual, lingual, disto-lingual) following the Silness-Loe Index.

Other effects on hard and soft tissue will also be recorded such as cervical abrasion, gingival abrasion and effect on dental restorations.

Toothbrushes: Oral B (A), BURST Oral care (B), manual toothbrush (C)

Dentifrice: Colgate Total

Duration of study: 32 days period

Baseline, data & Indices: oral prophylaxis will be performed to establish baseline scores to 0. Plaque indices and gingival indices (**Silness-Löe Index**) will be collected 24 hour prior to toothbrush delivery and the subjects will be instructed not to brush or use any device within this period. After the 24 hours abstinence period an initial G.I records will be collected prior to first use of the brushes followed by a second G.I record immediately after the first use of the toothbrush.

Sample Size: 90 healthy subjects age group 18-60 years old. Each group will contain 30 subjects.

Inclusion criteria

1. Good overall health
2. At least 20 teeth present, not including 3rd Molars
3. Non-smoker

Exclusion Criteria

1. Poor manual dexterity or mentally handicap;
2. Presence of removable intra-oral prosthesis
3. Current orthodontic therapy
4. Severe Periodontal condition or caries teeth in need of immediate attention
5. Pregnant women
6. Subjects that use medications that may effect oral health

7. No Systemic diseases/conditions such as diabetes mellitus, heart disease.
8. Use of plaque inhibiting toothpaste, mouthwash, interdental flossing in the period of the study

Subject Compensation

Study participants will receive \$100 for their participation. \$50 will be given at T2 and \$50 at T3.

Statistical Analysis

ANOVA:

- Compare the plaque level between the three groups after 30 days
- Compare the gingitis level between the three groups after 30 days

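### No capture of tissue effects between visits or after withdrawal is described, so short-lived gingival abrasions, and any tissue harm in subjects who leave, may be under-counted

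*Combined protocol and SAP*

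**What the plan says.** Materials and Methods commits to recording harm in one sentence: "Other effects on hard and soft tissue will also be recorded such as cervical abrasion, gingival abrasion and effect on dental restorations". It does not say when, by whom, at which sites, or how the effects are graded or counted.

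The rest has to be pieced together from nearby text in the same section:

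- **Follow-up visits:** "On the second visit at 14 days (T2) and third visit at 30 days (T3), additional GI and PI readings will be taken".
- **Examiner:** "All measurements and clinical examinations will be performed by a single blinded examiner".
- **First use at T1:** the pre-brushing readings are "followed by a second PI reading immediately after the first use of the power driven toothbrush". The Baseline, data & Indices paragraph calls this second reading a gingival one. On either account the examiner sees the mouth straight after the first brushing.
- **Exposure between visits:** "The subjects will be instructed to brush twice a day for a period of 2 minutes".
- **Size:** "Each group will contain 30 subjects".

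Statistical Analysis lists ANOVAs of plaque and gingivitis only, beginning with "Compare the plaque level between the three groups after 30 days". No table or comparison of tissue effects is planned. Subject Compensation pays $50 at each of T2 and T3. Nothing is said about subjects who do not return.

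**The concern.** Gingival abrasion is one of the three effects the plan names, and a soft-tissue abrasion can heal. Examination at T2 and T3 shows whether a lesion is present on those two days. It does not show whether the subject had one during 30 days of home use. A subject who stops attending because brushing hurts leaves no later examination, and the plan as written collects no reason.

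If the plan is followed as written, any resulting error in the number of abrasions is towards missing harm. A correct T1 baseline would not solve this: it separates old lesions from new ones, but cannot recover a lesion that came and went, or one in a subject who has left. Such events are hard to reconstruct once follow-up has ended.

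**Working it through.** The documents give no event rate, detection rate or healing time, so there is no stated figure to reproduce. The check takes the visit schedule from the plan and varies what the plan does not give.

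**Inputs from the plan.** Visits at days 14 and 30, so the gaps are 14 − 0 = 14 and 30 − 14 = 16 days. Brushing twice daily gives about 2 × 30 = 60 occasions, of which the observed first use at T1 is one. There are 30 subjects per arm.

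**Assumptions.** Onset is uniform over days 0 to 30. A lesion stays visible for D days.

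**Step 1: share of individual lesions present at T2 or T3.** A lesion is seen only if it starts within D days before a visit, so the share is [min(D, 14) + min(D, 16)] / 30.

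| D (days) | Calculation | Share seen |
|---|---|---|
| 3 | 6/30 | 20% |
| 7 | 14/30 | 47% |
| 10 | 20/30 | 67% |
| 14 | 28/30 | 93% |
| 16 or more | 30/30 | 100% |

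The last row is why lasting cervical abrasion or restoration damage is not missed through visit spacing in a subject who attends.

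**Step 2: subjects rather than lesions.** Suppose lesions recur as a Poisson process at rate λ per 30 days. The share of subjects with any lesion is 1 − exp(−λ). The share with at least one seen, at D = 7, is 1 − exp(−14λ/30). In an arm of 30:

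| λ | Subjects affected | Subjects seen | Ratio |
|---|---|---|---|
| 0.25 | 6.6 | 3.3 | 0.50 |
| 1 | 19.0 | 11.2 | 0.59 |
| 4 | 29.5 | 25.4 | 0.86 |

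The more often lesions recur, the smaller the per-subject shortfall.

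**Step 3: non-attendance.** If a fraction of subjects leaves before T2, for reasons unrelated to harm, the 47% is multiplied by one minus that fraction. Assumed losses of 5%, 10% and 20% give 44%, 42% and 37%. If the 10% leave between T2 and T3 instead, the share is 0.9 × 0.467 + 0.1 × 7/30 = 44%. One unrecorded harm-related withdrawal is 1/30 = 3.3 percentage points of an arm.

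**Step 4: the contrast between arms.** Assume true rates of 30% and 10%, and 47% detection in both arms. The observed rates are 0.30 × 0.47 = 14% and 0.10 × 0.47 = 5%. The ratio stays at 3, and the difference falls from 20 to 9.4 points. With 30 per arm and a two-sided 5% test of two proportions, power falls from 49% to 24%.

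**The case against.** The case against has several parts, and much of it stands.

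- **Silence is not exclusion.** A reader might infer that only the examiner can ever see these effects. The documents do not say so. The recording sentence is passive, and the examiner sentence does not rule out subject reports. Consent pages are not in the public file, so what subjects were told about reporting cannot be judged. What can be said is that no other capture is described, and an undescribed method cannot be counted on to be applied alike to 90 subjects.
- **T1 counts.** The reading after first use is a further chance to see an immediate effect. It does not cover the home brushing that follows.
- **The healing argument is narrow.** It applies to gingival abrasion, not to the two lasting effects. The withdrawal argument applies to all three.
- **There is no safety count to be wrong.** The purpose statement names no safety objective and no analysis is planned. A definite statement that the count is too low would go beyond the documents.
- **Arms.** A reader might infer that a harsher brush would look as safe as the others. Under equal detection it would not: the contrast shrinks and the ratio holds. Masking would need shorter-lived lesions or more harm-related loss in one arm, and the documents give no evidence of either.
- **Withdrawal.** A subject who stops the brush may still attend, and is paid to do so. One who leaves after T2 has been examined once in follow-up.
- **Limited gain.** Even with complete capture, power in the example above is only 49%. Better capture would not make 30 per arm a reliable safety comparison.

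None of this supplies a means of learning about a healed abrasion, or about why a subject left.

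**Conclusion.** The concern holds in a limited form. As written, the plan may under-count gingival abrasions that heal between visits, and tissue harm of any kind in subjects who stop attending. Per lesion, the share present at T2 or T3 is about 20%, 47% or 67% for visibility of 3, 7 or 10 days. That rests on uniform onset and an assumed healing time. Per subject, the ratio of seen to affected ranges from 0.50 to 0.86 at 7 days' visibility, depending on an assumed recurrence rate. The effect of loss to follow-up cannot be sized, because the plan gives no drop-out figure.

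The documents do not establish that a safety result is biased, or that the comparison between brushes is reversed or erased. The point concerns how an ancillary outcome is ascertained and does not touch the plaque and gingivitis analyses. It is still worth acting on, because the remedy is cheap and uses visits already planned.

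**What to change.** 1. State that the blinded examiner looks for gingival abrasion, cervical abrasion and restoration effects at T1 before and after first use, at T2 and at T3.
2. At T2 and T3, have someone other than the blinded examiner ask one fixed question about sore spots, gum injury or damaged restorations since the last visit, and record the dates. The plan names no such person, so it should designate the role.
3. For anyone who stops using the brush or misses a visit, record the date and reason, including any oral harm.
4. Tabulate, by randomised arm, the number of subjects with any event. Keep self-reports separate from blinded findings. Do not count bleeding alone as brush harm, because it overlaps with the gingivitis outcome.

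The cost is one question at two existing visits, a contact with each subject who misses a visit, and one table. No extra visit is needed. The drawback is that self-reports are unblinded and less specific than examination, which is why they are tabulated separately.

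### The only stated analyses are three-group ANOVAs at 30 days, so the plan gives no single-use or 14-day result and no estimate comparing any two brushes

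*Combined protocol and SAP*

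**What the plan says.** The title puts single use first: "A comparative study of electric toothbrushes for the efficacy of single use plaque removal". The purpose, in the introduction, is to "clinically evaluate the plaque removal efficacy of two electric powered toothbrushes". The same sentence then sets out the occasions and outcomes: "after a single use, as well as the effect on plaque accumulation and gingivitis after 14 days and 30 days period".

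The Toothbrushes entry lists three arms: A and B are the electric brushes and C is a manual brush. The Sample Size entry gives 90 subjects, 30 per group.

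The Statistical Analysis section is the word ANOVA and two bullets: "Compare the plaque level between the three groups after 30 days" and "Compare the gingitis level between the three groups after 30 days". It names no pairwise contrast, significance level, multiplicity rule or primary outcome.

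Readings at other times are planned. Materials and Methods schedules plaque index (PI) and gingival index (GI) before brushing at T1, "followed by a second PI reading immediately after the first use of the power driven toothbrush", and both indices again at 14 days (T2) and 30 days (T3).

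The allocation text reads: "The subjects will be randomized into 3 groups, and they will be provided one of the two evaluated toothbrushes".

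**The concern.** The stated analyses do not match the stated purpose in three ways.

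- **Coverage.** Single-use plaque removal, named first in both title and purpose, has no analysis. Neither has day 14.
- **Comparison.** A three-group F-test asks whether all three means are equal. It estimates neither A against B nor either electric brush against manual, and a significant result does not show which arm differs.
- **Ranking.** The two 30-day outcomes are listed side by side with no order, and any follow-up pairs are left open.

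Two things are at stake. A report that follows the plan literally would leave most of the purpose unanswered. A report that goes further would choose its pairs, and its analyses at the other times, after the data are seen.

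**Working it through.** **1. Coverage, from the text.**

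| Result named in the purpose | Reading scheduled? | Analysis stated? |
|---|---|---|
| Plaque removal, single use | Conflicting (see step 2) | No |
| Plaque, 14 days | Yes (T2) | No |
| Gingivitis, 14 days | Yes (T2) | No |
| Plaque, 30 days | Yes (T3) | Yes, three-group ANOVA |
| Gingivitis, 30 days | Yes (T3) | Yes, three-group ANOVA |

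The plan analyses two of five.

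**2. The single-use reading.** Materials and Methods makes the second T1 reading a PI, and describes it only for the power-driven brush. The Baseline, data & Indices entry makes the second record, right after first use, a GI. If that entry governs, there is no post-brushing plaque value to analyse. The Materials and Methods text leaves the manual arm's reading unclear.

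**3. The plan's own figure.** 3 × 30 = 90, which agrees. No power calculation can be reproduced, because alpha, power, effect size, SD and dropout are not stated. Everything below assumes two-sided alpha 0.05, full retention and effects in SD units.

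**4. What the F-test responds to.** With n = 30 per arm and df (2, 87), the noncentrality is λ = n Σ(μi − μ̄)². For means A = B = 0 and C = c, λ = 30 × (2/3)c² = 20c².

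| c (SD) | λ | F-test significant | F-test significant, direct A-B test not |
|---|---|---|---|
| 0.3 | 1.8 | 20% | 16% |
| 0.5 | 5.0 | 49% | 44% |
| 0.8 | 12.8 | 89% | 84% |
| 1.0 | 20.0 | 98% | 93% |

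The last column is from 1,000,000 simulated trials. None of these percentages is an error rate: the arms do differ, so the F-test is right to reject. They show how often a positive result would come from the manual arm while A and B are identical.

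**5. Error control if A-B is tested only after a significant F-test (one outcome, A = B).** The simulated false-positive rate for A-B is 0.025, 0.036, 0.045, 0.050 and 0.050 at c = 0, 0.3, 0.5, 0.8 and 1.0. It does not exceed the nominal 5%.

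**6. Power for A-B.** The detectable difference at 80% power is close to √(2/30) × (t for 1 − α/2 + t for 0.80), with 87 df. At α = 0.05 this is 0.2582 × (1.988 + 0.846) = 0.73 SD. At that difference:

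| Position of C | F-test power | A-B power, tested directly | A-B power, gated by F-test |
|---|---|---|---|
| Midway between A and B | 0.70 | 0.80 | 0.69 |
| Equal to A or B | 0.83 | 0.80 | 0.76 |
| 1.0 SD from A, on B's side | 0.95 | 0.80 | 0.79 |
| 1.5 SD from A, on B's side | – | 0.80 | 0.80 |

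**7. Precision.** The 95% CI half-width for A-B is 1.988 × √(2/30) = 0.51 SD.

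**The case against.** Pairwise tests normally follow an ANOVA, and nothing in the plan rules them out. That is fair, and step 5 shows that gating A-B behind the F-test is valid for one outcome. A reader might infer from the large percentages in step 4 that the ANOVA produces false claims about the electric brushes; the calculations do not support that. What stands is that the pairs are not named and no estimate is planned.

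A reader might also infer that the trial's aim is plainly A against B and that the analysis misses it. The documents do not go that far. The title leans that way, but the purpose says only that the two brushes will be evaluated. A manual arm is randomised, and the background says that many adults "find thorough toothbrushing with a standard manual toothbrush to achieve a plaque-free state challenging". Electric against manual is therefore a credible aim. The F-test estimates neither comparison, so the gap remains on both readings.

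It could be said, too, that the plan has no lead time point. Strictly, day 30 leads by default, because it is the only time analysed. The gap is the mismatch with a purpose that puts single use first.

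Finally, one might assume that every reading needed is already scheduled. That holds for days 14 and 30 but, given the PI/GI conflict, not safely for single use.

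**Conclusion.** The point holds as a mismatch between purpose and analysis, not as an invalid test. Three of the five outcome-time results have no stated analysis, including the one named first. The two that are analysed yield an overall test with no estimate for any pair of brushes. The two outcomes are unranked and follow-up pairs are open.

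The count of two out of five rests on the text alone. The power figures rest on assumed alpha, assumed effects and full retention, and are illustrations. Testing a named contrast directly is preferable for power: 0.80 against 0.69 with manual midway, and a negligible difference when manual is far from both. It does not correct an error. The plan should be changed, but the ANOVA remains valid for its own hypothesis.

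**What to change.** 1. **Add the missing analyses.** Specify the pre- to post-brushing change in PI at T1 for single use, and plaque and gingivitis at day 14, with estimates and 95% CIs. Name one lead outcome and time point and make the rest secondary.
2. **Settle the single-use reading first.** Reconcile Materials and Methods (second reading is PI, after the power-driven brush) with Baseline, data & Indices (second record is GI). Confirm that post-brushing plaque is read in all three arms. Until then, single use can neither be analysed nor lead.
3. **Name the contrasts.** From the three-group model, report all three pairwise differences with 95% CIs. If the aim is to compare the electric brushes, make A-B primary, tested directly at two-sided 5%. If the aim is electric against manual, make A-C and B-C primary with Holm. The sponsor must confirm which.
4. **Set multiplicity.** If both 30-day outcomes stay primary, apply Holm across all primary tests: two for the A-B aim, four for electric against manual.
5. **Reconcile the allocation sentence**, which mentions two evaluated brushes, with the three arms.

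**Cost.** For days 14 and 30 the change is plan wording only, with no added subjects or visits. Single use depends on item 2. Keeping two primary A-B tests raises the difference detectable with 80% power at the strictest Holm step (0.025) from 0.73 SD to 0.2582 × (2.281 + 0.846) = 0.81 SD. With Holm on A-C and B-C for one outcome, and manual 0.8 SD from both brushes, both contrasts are significant in 77% of trials and at least one in 91%, against 87% for each if unadjusted.

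### Both planned ANOVAs use only the day-30 score, so subjects without a T3 reading drop out despite their T1 and T2 scores; if loss is related to plaque or gingival status, the completer comparison can be biased.

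*Combined protocol and SAP*

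**What the plan says.** The Statistical Analysis section names one method, ANOVA, and two uses of it: "Compare the plaque level between the three groups after 30 days" and "Compare the gingitis level between the three groups after 30 days".

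More is measured than is analysed. Materials and Methods states for the first appointment: "At T1 initial GI and PI will be taken prior to brushing followed by a second PI reading immediately after the first use". For the later visits it states: "On the second visit at 14 days (T2) and third visit at 30 days (T3), additional GI and PI readings will be taken". The stated purpose covers single use and "the effect on plaque accumulation and gingivitis after 14 days and 30 days period".

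On size, the plan gives "Sample Size: 90 healthy subjects age group 18-60 years old" and "Each group will contain 30 subjects". It says nothing about missing readings, withdrawals, imputation, analysis population, expected loss or replacement of subjects.

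**The concern.** An ANOVA of a day-30 score needs a day-30 score. The plan does not say in words that a subject who misses T3 is excluded, but with no substitute for the missing value nothing else can happen. The comparison is then among those who attended T3, which need not be the groups as randomised.

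The trial is single-blind with a blinded examiner, and a subject can see whether the brush is manual or powered, so loss that differs by arm is possible. If higher (worse) scorers leave one arm more often, that arm's day-30 mean looks better than it should. The T2 reading, taken by the same examiner, carries information about the missing T3 value, and the plan sets it aside.

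**Working it through.** **1. The plan's own figure.** 3 groups x 30 = 90 agrees. The basis for 90 cannot be reproduced, because no alpha, power, effect size or SD is stated. For scale only, assuming two-sided alpha 0.05 and 80% power, the detectable pairwise difference is (1.960 + 0.842) x sqrt(2/30) = 0.72 SD.

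**2. Bias formula, no true difference, loss in one arm only.** Let x be the standardised T2 score (higher is worse) and T3 = r·x + sqrt(1 − r²)·e. Let the probability of leaving after T2 be p(x) = 1/(1 + exp(−(a + b·x))), with a set to give overall loss L. The mean T2 score of those who stay is m = ∫ x·[1 − p(x)]·φ(x) dx / (1 − L), and the bias in that arm's day-30 mean is r·m. The values of L, b and r are assumptions.

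| slope b | loss L | a | m (SD) | bias, r = 0.5 | bias, r = 0.7 |
|---|---|---|---|---|---|
| 0.5 | 3% | −3.593 | −0.015 | −0.007 | −0.010 |
| 0.5 | 10% | −2.295 | −0.049 | −0.024 | −0.034 |
| 0.5 | 20% | −1.459 | −0.096 | −0.048 | −0.067 |
| 1.5 | 3% | −4.448 | −0.040 | −0.020 | −0.028 |
| 1.5 | 10% | −2.953 | −0.122 | −0.061 | −0.085 |
| 1.5 | 20% | −1.916 | −0.227 | −0.113 | −0.159 |

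The range is thus about 0.01 to 0.16 SD, in favour of the arm with losses. Simulation with 30 per arm and 20,000 trials per scenario agrees at slope 1.5: −0.059 and −0.086 SD at 10% loss, −0.114 and −0.160 SD at 20%, for r = 0.5 and 0.7.

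**3. Using T2.** In those four scenarios a likelihood estimate that also uses T2 has bias 0.002, 0.000, 0.000 and −0.001 SD. Its standard errors are 0.263 to 0.273 SD, against 0.262 to 0.272 SD for completers. As a check, sqrt(1/30 + 1/30) = 0.258 with no loss and sqrt(1/24 + 1/30) = 0.274 with 20% loss in one arm.

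**4. When a true difference exists.** Take a true difference of −0.72 SD, slope 1.5 and r from 0.3 to 0.7, with the same score-related loss rule in both arms. The worse arm then loses 17% to 27% and the better arm 8% to 14%. The completer difference is −0.69 to −0.63 SD, a shrinkage of 0.03 to 0.09 SD. The T2-using estimate stays at about −0.72 SD.

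**5. When there is no bias.** With no true difference and the same loss rule in every arm, the completer difference is within 0.004 SD of zero and the three-arm ANOVA type I error is 4.8% to 5.3%. With completely random loss, the completer difference stays at about −0.72 SD and only power falls.

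**6. Type I error when loss differs by arm.** With slope 1.5, r of 0.5 to 0.7 and 10% loss in one arm only, it is 5.5% to 5.9% against a nominal 5%. It is about 8% at 20% loss with r = 0.7. A heavier case, with score-related loss of 17% or 27% in one arm, random loss of 10% or 20% in the others and r = 0.7, gives 7.2% or 10.1%.

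**The case against.** The strongest reply is that little may be lost. T2 and T3 are 30 − 14 = 16 days apart, subjects are healthy, severe periodontal conditions are excluded, and half the payment ($50 of $100) is made at T3. Loss of 1 or 2 of 30 subjects in one arm (3% to 7%) gives a bias of only 0.02 to 0.06 SD even at slope 1.5, well inside the standard error. That slope is itself steep: exp(1.5) = 4.5, so the odds of leaving rise about 4.5-fold per SD. All of this stands, and is why the range must run down almost to zero.

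A reader might infer four stronger things that the documents do not support:

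- **That status-related loss always biases the comparison.** It does so only if the loss pattern differs by arm or there is a true group difference (steps 4 and 5).
- **That a subject who stops using the brush is excluded.** Nothing ends that subject's visits. If T3 is attended, there is a score and it can enter the ANOVA.
- **That the manual arm would lose its worst scorers and so hide an electric-brush advantage.** The introduction says many adults find thorough manual brushing hard. No text says manual-brush subjects are more likely to leave, links a T2 score to leaving, or says that scores are disclosed to subjects.
- **That a mixed model removes the problem altogether.** The near-zero bias in step 3 arises because the simulation made loss depend only on T2.

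The reply does not remove the central point. T2 and T1 readings are taken and left unused, and without a rule the handling of missing readings would be chosen after the data are seen.

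**Conclusion.** The point holds in conditional form. By construction both ANOVAs exclude subjects without a T3 reading, and the comparison can then be biased if loss is related to status and either differs by arm or accompanies a true difference. Over the assumed range, the bias is about 0.01 to 0.16 SD. At its largest it is 0.16/0.27 = 0.6 of a standard error; at its smallest it is negligible. The size cannot be fixed from the documents, which give no loss rate, SD, correlation or loss mechanism, and no direction by arm can be claimed. This is a change that should be made because it is cheap, not because the plan is shown to produce a wrong answer.

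**What to change.** Replace each day-30 ANOVA with a repeated-measures mixed model, one for PI and one for GI, on T2 and T3, with group, visit, group-by-visit and an unstructured covariance. Use the T1 pre-brushing score as well, either as an outcome or as a covariate by visit; as an outcome, it also keeps subjects seen only at T1. Include every randomised subject with at least one reading, in the assigned group, and take the three-group day-30 comparison from the model. Record T2 and T3 readings for subjects who stop using the brush, and report losses by arm with reasons.

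The cost is a few lines of statistical wording and slightly more analysis work, with no new visit or measurement. With no losses, the T2/T3 model gives essentially the ANOVA's day-30 answer. The limit should be stated in the plan: the model corrects only loss explained by observed scores, not loss driven by unobserved status, and a subject lost before T2 contributes at most T1 data.

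### The two day-30 ANOVAs leave out the pre-brushing T1 reading; they are valid but may waste precision, and the baseline reading is described inconsistently

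*Combined protocol and SAP*

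**What the plan says.** The Statistical Analysis section names one method, ANOVA, and two comparisons: "Compare the plaque level between the three groups after 30 days" and "Compare the gingitis level between the three groups after 30 days". It mentions no covariate, change score or baseline value.

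Materials and Methods describes the measurements twice.

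- **Visit description (study design text).** Prophylaxis at T0 is meant "to ensure a baseline of 0 Plaque Index (PI) prior to the first appointment (T1"). Subjects then do not brush "until the initial PI and Gingival Indexes (GI) are taken at 24 hours after T0". At that visit, "At T1 initial GI and PI will be taken prior to brushing followed by a second PI reading immediately after the first use". So both indices are read before brushing, and PI is read again afterwards.
- **Paragraph headed Baseline, data & Indices.** Prophylaxis again sets baseline scores to 0. PI and GI "will be collected 24 hour prior to toothbrush delivery". After the 24-hour abstinence, "an initial G.I records will be collected prior to first use of the brushes", and the second reading after first use is also GI. PI is not mentioned at this point.

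The sample size is 90, with 30 per group. No power calculation, effect size, SD or significance level is given.

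**The concern.** A reading taken before first brush use cannot be affected by the assigned brush. If it predicts the day-30 score, adjusting for it removes that part of the between-subject variation and narrows every day-30 comparison without adding a subject. The plan collects such a reading and does not use it. Since 90 subjects are not justified by any power calculation, nothing shows that the trial has precision to spare.

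Whether adjustment is possible for plaque depends on which reading is the baseline. Under the visit description, T1 PI is 24-hour regrowth and varies between subjects. Under the baseline paragraph, PI could be read 24 hours before delivery, at about the time of prophylaxis, when the aim is a score of 0. Staff who follow that paragraph might never record PI at T1 before brushing.

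**Working it through.** **Inputs from the documents.** Three arms, 30 per arm (3 × 30 = 90, which agrees with the stated total); randomised parallel design; analysis at day 30. The figure of 90 cannot be reproduced further, because the inputs to a power calculation are not stated.

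**Assumptions.** Two-sided 5% level; all 90 subjects complete; one summary score per subject; T1-to-day-30 correlation ρ of 0, 0.3, 0.5 or 0.7. For power only, one arm differs from the other two by 0.6 SD. SD means the within-arm SD of the day-30 score.

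**Precision.** ANOVA has 90 − 3 = 87 error degrees of freedom; ANCOVA with one covariate has 86. Including the cost of estimating the slope, the variance of an adjusted difference is the unadjusted variance multiplied by

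V = (1 − ρ²) × (1 + 1/85).

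At ρ = 0.5, V = 0.75 × 1.0118 = 0.759. The equivalent sample size is 30/0.759 = 39.5 per arm and the standard error ratio is √0.759 = 0.871.

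CI half-width for two arms:

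- Unadjusted: t(87) × √(2/30) = 1.988 × 0.2582 = 0.513 SD.
- Adjusted: t(86) × √(2V/30). At ρ = 0.5 this is 1.988 × 0.2582 × 0.871 = 0.447 SD.

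**Power of the three-group F test.** Arm means of 0.6, 0.6 and 0 have a grand mean of 0.4 and squared deviations summing to 0.04 + 0.04 + 0.16 = 0.24. The noncentrality is 30 × 0.24 = 7.2 unadjusted and 7.2/V adjusted (9.49 at ρ = 0.5).

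| | Unadjusted | ρ = 0 | ρ = 0.3 | ρ = 0.5 | ρ = 0.7 |
|---|---|---|---|---|---|
| Standard error ratio | 1 | 1.006 | 0.960 | 0.871 | 0.718 |
| Equivalent n per arm | 30 | 29.7 | 32.6 | 39.5 | 58.1 |
| CI half-width (SD) | 0.513 | 0.516 | 0.493 | 0.447 | 0.369 |
| F-test power | 65.2% | 64.7% | 69.1% | 77.8% | 91.8% |

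**Break-even.** V = 1 when ρ² = 1 − 85/86, so ρ = 0.108. Below that, adjustment costs at most 0.6% in standard error.

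**Validity.** In 20,000 simulated null trials per setting, type I error was 4.8% to 5.1% for both methods.

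**Sensitivity to the assumed effect.** If the effect is instead set so that the unadjusted F test has 80% power, and the small slope-estimation cost is ignored, adjusted power is 83.8%, 90.4% and 98.0% at ρ = 0.3, 0.5 and 0.7. With the slope cost included and ρ = 0.5, the gain is about 5 points at 0.3 SD (20% to 25%), 13 at 0.6 SD, 7 at 0.8 SD and 1.5 at 1.0 SD. The CI widths do not depend on the effect.

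**Chance imbalance.** A T1 gap of 0.3 SD between two arms leaves ρ × 0.3 in the unadjusted day-30 difference: 0, 0.09, 0.15 or 0.21 SD. Since 0.3/0.2582 = 1.16, a gap larger than 0.3 SD has a 24.5% chance for a given pair; for at least one of three pairs it is about 48%. This is the same loss of precision seen within a single trial, not an additional bias.

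**The case against.** The strongest reply is that an unadjusted comparison in a randomised trial is legitimate and the gain is conditional. T1 PI is one day of unbrushed regrowth after plaque was reset, whereas day-30 PI follows a month of twice-daily brushing, with no abstinence stated before T3. The two may correlate weakly. At ρ = 0.2 the half-width moves only from 0.513 to 0.506 SD and power from 65.2% to 66.6%. The 0.6 SD effect is also an assumption, and it lies near where the power gain is largest.

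These cautions stand, and they are why the point concerns efficiency rather than error and why CI widths are the better measure. They do not remove it. At the low end almost nothing is lost by adjusting; at ρ of 0.5 or more the gain is material.

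A second reply is that the visit description already specifies a usable covariate. It does, but the baseline paragraph contradicts it, and not only before brushing: the reading after first use is PI in one place and GI in the other.

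A qualification also stands. Calling the ANOVA valid presumes one score per subject. The plan records six teeth at six sites each (36 sites) and names no subject-level summary. Treating sites as independent observations would not be valid.

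**Conclusion.** The concern holds. Both planned ANOVAs omit a pre-treatment reading that the visit description collects. With one score per subject they remain valid, so what is at stake is precision. The gain is small at ρ of 0.3 or below (half-width 4% narrower at 0.3) and material from about 0.5 (13% narrower, equivalent to about 39.5 rather than 30 subjects per arm). These sizes rest on assumed correlations and full completion; the power figures rest also on the assumed 0.6 SD difference. The inconsistency in the baseline description needs no assumption: it is in the text, and it decides whether adjustment is possible for plaque at all. The change should be made. Confidence in the size of the benefit is only medium, because the correlation is unknown.

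**What to change.** 1. In Statistical Analysis, replace each ANOVA with an ANCOVA of the subject's mean day-30 PI (or GI) on arm, with the same index at T1 before brushing as covariate. Keep the three-group F test and report adjusted arm differences with 95% CIs. Fix this before outcome data are seen. The reading taken after first use must not be the covariate, because the assigned brush affects it.
2. Name the T1 reading after the 24-hour abstinence and before first brush use as the baseline for both indices.
3. Rewrite the Baseline, data & Indices paragraph to agree with the visit description: both PI and GI recorded at that point, the timing relative to toothbrush delivery made clear, and the index re-read after first use stated consistently.

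The cost is wording and one error degree of freedom. Under the visit description no new measurement is needed; under the baseline paragraph, collection of PI at T1 before brushing must be confirmed. If the covariate proves uninformative, the penalty is a 0.6% larger standard error.
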